## **Blood handling**

#### Phase I

Each participant in the control arm will donate 5 ml of blood (1 x 5 ml serum). Each participant in experimental arm will donate 10 ml of blood (2 x 5 ml EDTA). Blood sampling will be done by professional phlebotomists at Unilabs or at the primary care unit.

# Phase II

Each research participant will donate 15 ml of blood (1 x 5 ml serum + 2 x 5 ml EDTA). Blood sampling will be done by professional phlebotomists at Unilabs or at the primary care unit.

# Project description, Phase I

#### **Step 1: Cluster randomization**

Participating primary care units will be 1:1 cluster randomized to either control or experimental arm. For randomization procedure, please see section *Randomization Procedure* above.

#### Step 2: Recruitment, consent, and blood sampling

Men with no previous prostate cancer diagnosis, eligible for prostate cancer test according to standard of care and meeting the study inclusion/exclusion criteria, will be offered to participate in the study.

Men that are interested and have read the *Research Participant Information* will sign an informed consent. Men that are not interested to participate in the study will be offered standard of care.

The physician orders PSA (control arm) or Stockholm3 (experimental arm) from Unilabs' catalog. The research participant proceeds to the sampling unit, where blood is collected for PSA (control arm, 1 x serum tube) or Stockholm3 (experimental arm, 2 x EDTA tubes). The samples are transported to Unilabs in Solna/Huvudsta.

#### Step 3: Lab analysis

Samples are received at Unilabs in Solna/Huvudsta.

Samples from primary care units are processed for PSA (control arm) or PSA and Stockholm3 if PSA ≥1.5 ng/ml (experimental arm) and the result is reported to the ordering physician.

#### Step 4: Clinical decision based on lab results

Based on the result from the PSA or Stockholm3 analysis, the man is handled in accordance with clinical practice at the participating primary care unit. This means that the doctor will take decision whether to send men with elevated PSA (PSA  $\geq$  3 ng/ml, control arm) or elevated Stockholm3 (Stockholm3  $\geq$  11, experimental arm) for further examination with MRI Men with positive MRI (PIRADS  $\geq$  3, both arms) should be offered prostate biopsy based on current standard of care.

## **Step 5: Data collection**

Data will be collected prospectively by medical record analyses to see if the man was referred to MRI and/or prostate biopsy, and if so, the results from these procedures (Grade Group and PIRADS) will be collected. Unilabs will provide a list of all PSA tests at participating primary care units. Data on percentage of Gleason Grade 4, mm cancer, type of biopsy, instrument used will be collected from analyses of pathology reports. Data on type of MRI protocol and MRI instruments will be collected from analysis of radiation reports.

Karolinska Institutet will enter data into a study database and evaluate the results.

MRI and biopsies performed within 4 months from test results delivered to physician will be included in the analysis.

# Step 6: Statistical analysis

A Statistical Analysis Plan (SAP) will be developed and published before the start of the study. In summary, we will apply the following statistical analyses:

#### Primary outcomes:

• We will use a generalized linear mixed model (GLMM) with a log-link function and binomial distribution test to for differences in detection rates of csPC. Mixed effect models explicitly incorporate cluster-level random effects, ensuring accurate estimation of intervention effects and their standard errors. Results will be presented as risk ratios (RRs) or risk differences (RDs) with corresponding confidence intervals, adjusting for randomization stratification variables. Cluster-level random intercepts will account for within-cluster correlations. In the event of convergence issues, a modified Poisson regression model with robust standard errors will be used as a backup strategy.

Superiority testing will be conducted to assess whether the Stockholm3-based diagnostic pathway detects a significantly higher number of clinically significant prostate cancers (csPC) compared to the standard PSA-based pathway. The null hypothesis ( $H_0$ ) assumes that both diagnostic strategies have equal detection rates, whereas the alternative hypothesis ( $H_1$ ) assumes that the Stockholm3 pathway results in a higher detection rate. 95% confidence intervals for effect size estimates will be reported.

- Socioeconomic status (CNI, Care Need Index) of the participating site's catchment area (low, medium, high)
- Annual PSA testing volume at the participating site (low, medium, high)

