# Study size and outcome

#### Phase I

We assume individual randomization and an effect size of a 40-50% increase in csPC detection (4% in the control arm vs. 5.6-6.0% in the experimental arm), a 5% significance level, 80% power, an average sample size per cluster of m=100-150 men, and an intracluster correlation coefficient ( $ICC = Between-cluster\ variance / (Between-cluster\ variance + Within-$ 

cluster variance) of 0.005-0.01. The ICC measures how similar outcomes from individuals within the same cluster are, compared to individuals from different clusters. It thus quantifies the extent to which outcomes "cluster together" within participating sites. Following Rutterford et al. [8], a sample size of 8,000 men then provides in the range of 58-92% power. Specifically, using plausible values of an effect size of 45%, m=100, and an ICC of 0.008 gives 80% power with 8,000 recruited men.

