#### Randomization procedure

Recruitment will take place at more than 30 primary care units across Sweden. To participate in the study, primary care units must use Unilabs as their laboratory service provider.

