# Secondary outcomes:

- A generalized linear mixed model (GLMM) with a log-link function and binomial distribution to test for differences in compliance
- Descriptive statistics for MRI and biopsy rates
- Detection of clinically significant prostate cancer at different PSA ranges
- Operating characteristics of PSA and Stockholm3 to predict csPC at different PSA and Stockholm3 cut-offs
- Operating characteristics of PSA and Stockholm3 to predict abnormal MRI (defined as PIRADS ≥3) at different PSA and Stockholm3 cut-offs
- Operating characteristics of PSA and Stockholm3 to predict abnormal MRI (defined as MRI that led to csPC) at different PSA and Stockholm3 cut-offs
- Unnecessary biopsies/MRIs: a normal MRI based on prostate imaging reporting and data system (PIRADS) (I.e. PIRADS 1, 2 and without lesion), benign pathology on biopsy, or low grade ISUP 1 cancer (aka, Grade Group 1, Gleason Score 3+3, Gleason Score 6)
- Adjusted analyses based on potential confounders (e.g., age, PSA levels)
- Healthcare utilization of resources (#MRI, #Biopsy, #ISUP grade group 1 cancers detected)

Randomization stratification factors will be included as covariates in the regression models used for analysis. Data analysis will be performed by the PI or key research personnel. An independent Data Analysis Committee headed by [name] will be overseeing the data analysis.

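### Phase I: the protocol's assurance that the mixed model gives accurate standard errors is too strong; uncorrected inference would run at about 6–7% with the 53–80 units implied by the sample size, and about 9% if only about 30 join

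*Protocol*

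**What the plan says.** Under Project description, Phase I, Step 6 (Primary outcomes), the protocol plans a log-link binomial GLMM with random intercepts for primary care units, adjusted for the randomization strata. It adds this assurance: "Mixed effect models explicitly incorporate cluster-level random effects, ensuring accurate estimation of intervention effects and their standard errors". The backup, if the model does not converge, is modified Poisson regression with robust standard errors. No test statistic, reference distribution, degrees of freedom or small-sample correction is named for either model.

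The strata are Care Need Index and annual PSA testing volume, each in three levels and each a property of the site. The Secondary outcomes text confirms the adjustment: "Randomization stratification factors will be included as covariates in the regression models used for analysis".

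Two places bear on the number of units:
- Randomization procedure, before the text divides by phase: "Recruitment will take place at more than 30 primary care units across Sweden".
- Study size and outcome, Phase I: "a 5% significance level, 80% power, an average sample size per cluster of m=100-150 men". With 8,000 men this fixes an implied number of units.

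The alternative hypothesis is directional (it "assumes that the Stockholm3 pathway results in a higher detection rate"), but the text does not say whether the test is one- or two-sided.

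**The concern.** A mixed model accounts for clustering, but that alone does not make its standard errors accurate when units are few. Units are randomized whole, so information on the arm effect comes from differences between units. Intercept, arm and two dummies for each stratification factor make 1 + 1 + 2 + 2 = 6 fixed parameters, all at unit level. Maximum likelihood estimates the between-unit variance without allowing for those six, so the estimate is too low and normal-theory tests and intervals are too narrow. More men per unit do not cure this.

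At stake are the type I error of the Phase I superiority claim and the coverage of its 95% CI. The protocol allows Phase I to be published before Phase II starts, so the result may stand alone. The sentence also does harm by its place in the text: it tells whoever writes or codes the analysis that nothing more is needed.

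**Working it through.** **Inputs from the protocol.** 8,000 men; csPC "4% in the control arm vs. 5.6-6.0% in the experimental arm"; 5% significance level; m = 100–150; ICC 0.005–0.01; two three-level unit-level covariates; 1:1 stratified block allocation of units.

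**Assumptions added.** Two-sided test (it reproduces the stated power), maximum likelihood fit, blocks of 2, log-normal unit effects matched to the ICC, and equal unit sizes unless stated.

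**Step 1. Reproduce the protocol's power.** Its central case is "using plausible values of an effect size of 45%, m=100, and an ICC of 0.008 gives 80% power with 8,000 recruited men".
- Design effect = 1 + (m − 1) × ICC = 1 + 99 × 0.008 = 1.792.
- Effective men per arm = 4,000 / 1.792 = 2,232.
- Two proportions, 4% vs 5.8%, two-sided 5%: power 79.6% (stated 80%).
- Extremes: 56.4% (40% effect, m = 150, ICC 0.01) and 91.9% (50% effect, m = 100, ICC 0.005), against a stated 58–92%.

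The inputs are therefore read as the protocol meant them.

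**Step 2. Number of units.** 8,000 / 150 = 53 and 8,000 / 100 = 80. Thirty units would need 8,000 / 30 ≈ 267 men each, outside the stated m.

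**Step 3. Type I error with no true effect.** The log-binomial random-intercept model was fitted by maximum likelihood (31-point Gauss–Hermite quadrature) with arm and the four stratum dummies. There were 5,000–8,000 simulated trials per case; Monte Carlo standard error is about 0.3–0.4 points.

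| Units | Wald z | Likelihood ratio | Mean model SE / true SD |
|---|---|---|---|
| 30 | 8.6–9.6% | 7.9–8.9% | 0.87–0.88 |
| 53 | 6.6–7.1% | 6.2–6.7% | 0.93–0.95 |
| 80 | 6.0–6.8% | 5.8–6.5% | 0.95–0.96 |

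Between 30 and 53, 36 units give 7.7–7.9% and 40 units give 8.2% (Wald z).

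**Step 4. What drives it (ICC 0.008).**
- Dropping the four stratum terms lowers the Wald error from about 9% to 6.6% at 30 units.
- The factor √((K−6)/K) is 0.894 at 30 units, 0.942 at 53 and 0.962 at 80. This is close to the simulated standard-error ratios, as expected if the six parameters are the cause.
- Unequal unit sizes (CV 0.6, assumed) give 9.8% at 30 units, 7.7% at 53 and 6.1% at 80.
- The uncorrected robust z test of the backup gives 9.5–9.9% at 30 equal units and 12.6% at 30 units with CV 0.6.

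**Step 5. Corrections (ICC 0.008, equal sizes).**

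| Units | t(K−6) on the ML SE only | SE × √(K/(K−6)) with t(K−6) | Cluster-level regression, t(K−6) |
|---|---|---|---|
| 30 | 8.1% | 5.4% | 5.1% |
| 53 | 6.4% | 5.1% | 5.0% |
| 80 | 5.6% | 4.8% | 4.8% |

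Changing only the reference distribution is not enough at 30 units; the standard error itself has to be corrected.

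**The case against.** The strongest reply is that the protocol only summarizes the analysis and leaves detail to a SAP to be published before the start. Estimation method, degrees of freedom and small-sample corrections are usual SAP content, and that SAP may already contain them. This stands as far as it goes: the absence of a named correction is not a finding. The affirmative sentence is different. It is in the protocol, it concerns the primary analysis, and it is wrong for the default fit whatever the SAP adds. One can read it as merely explaining why random effects are used, but it expressly extends to standard errors.

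A second reply is that the inflation is modest. For the trial as sized, that is right. A reader might infer from the figure of 30 units that the primary test runs at close to twice its nominal level. The documents do not support this as the headline. The figure is a lower bound in a section common to both phases, while the Phase I sizing implies 53–80 units. Nor does the protocol commit to a Wald test; a likelihood ratio test does slightly better, though it too exceeds 5%.

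It is also fair to say that if only about 30 units joined, power would be the larger problem. With m ≈ 267 the design effect is 1 + 265.7 × 0.008 = 3.125, and power at a 45% effect is 56%. That is a separate reason to reconcile the two sections on the number of units.

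**Conclusion.** The point holds at moderate size. The assurance overstates what ordinary maximum likelihood delivers: the standard error was too small at every unit count tried, and the planned stratum adjustment adds to this. An uncorrected two-sided 5% Wald test runs at about 6–7% with the implied 53–80 units and at about 9% near the floor of 30.

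These sizes assume 8,000 men, 4% csPC, ICC 0.005–0.01, equal unit sizes, blocks of 2 and an uncorrected test. Unequal sizes can raise them, to 7.7% at 53 units with a CV of 0.6. If the SAP already specifies an adequate correction, only the wording of the protocol and its agreement with the SAP remain to be settled. The flaw does not invalidate the design, but it touches the primary claim and is cheap to remove, so it should be fixed.

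**What to change.** Delete the assurance about accurate standard errors and state the small-sample inference for the Phase I primary comparison, so that estimate, p-value and 95% CI come from one analysis. With K the number of units randomized and analysed, either of these will do:

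1. Keep the GLMM and its risk ratio, multiply the standard error by √(K/(K−6)), and use t on K−6 df for both test and interval. This is the smaller change.
2. Use a stratum-adjusted cluster-level analysis with t on K−6 df for both estimate and interval. The version checked here regresses unit proportions, so it estimates a risk difference that weights units equally.

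Do not pair a GLMM estimate with a cluster-level interval: with unequal units the two weight the data differently. Give the modified Poisson backup a small-sample correction as well. State whether the test is one- or two-sided, and reconcile the floor of 30 units with the 53–80 implied by the sample size. The corrections were checked with equal unit sizes, so repeat the simulation once the likely spread of sizes is known.

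The cost is wording, a few lines of code and a slightly wider interval. For the 45% effect at ICC 0.008, replacing the normal reference by t on K−6 df lowers power from 79.6% to 78.6% with 80 units (about 1 point) and from 56% to 53% with 30 (about 3 points).

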# Secondary outcomes:

- A generalized linear mixed model (GLMM) with a log-link function and binomial distribution to test for differences in compliance
- Descriptive statistics for MRI and biopsy rates
- Detection of clinically significant prostate cancer at different PSA ranges
- Operating characteristics of PSA and Stockholm3 to predict csPC at different PSA and Stockholm3 cut-offs
- Operating characteristics of PSA and Stockholm3 to predict abnormal MRI (defined as PIRADS ≥3) at different PSA and Stockholm3 cut-offs
- Operating characteristics of PSA and Stockholm3 to predict abnormal MRI (defined as MRI that led to csPC) at different PSA and Stockholm3 cut-offs
- Unnecessary biopsies/MRIs: a normal MRI based on prostate imaging reporting and data system (PIRADS) (I.e. PIRADS 1, 2 and without lesion), benign pathology on biopsy, or low grade ISUP 1 cancer (aka, Grade Group 1, Gleason Score 3+3, Gleason Score 6)
- Adjusted analyses based on potential confounders (e.g., age, PSA levels)
- Healthcare utilization of resources (#MRI, #Biopsy, #ISUP grade group 1 cancers detected)

Randomization stratification factors will be included as covariates in the regression models used for analysis. Data analysis will be performed by the PI or key research personnel. An independent Data Analysis Committee headed by [name] will be overseeing the data analysis.

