# **Primary endpoint measures**

• Number of csPC, defined as Grade Group ≥ 2

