#### Phase I design

Phase I will compare the clinical utility of using PSA based diagnostics versus using Stockholm3 as a reflex to PSA ≥ 1.5 ng/ml. Participating primary care units will be 1:1 cluster

randomized between control arm with standard of care (SOC) with PSA or experimental arm with Stockholm3 as a reflex to PSA  $\geq$  1.5 ng/ml. Cluster randomization was chosen for this study phase to prevent potential contamination between intervention and control groups. Individual randomization could lead to participants in the control arm unintentionally receiving components of the intervention through interactions with participants in the intervention group. We hypothesize that the use of Stockholm3 improves both test characteristics and the operational structure in the healthcare system (e.g. compliance with test recommendations) compared with today's standard of care. While the effect of better test characteristics is possible to study using individual randomization (see Phase II), the improved operational structure requires cluster randomization to avoid spill-over effects. By randomizing at the cluster level, we thus ensure clearer separation between treatment arms to study the *combined* effect of test characteristics and operations.

This study phase is unblinded for both investigators and participants. Participating primary care units will be cluster-randomized at the study start to either the control or experimental arm. Primary care physicians will recruit men they consider eligible for prostate cancer testing, following standard clinical practice. The decision to refer participants for specialist evaluation, including MRI and biopsy, will be made by the primary care physician in accordance with standard clinical practice

**Primary Care** Primary Care Specialist care Laboratory Control Arm Analysis Recruitment sampling of PSA on referral Eligible and Sampling of Decision on referral at consenting participants in the doctor's Decision primary care discretion R Workup on workup No previous PC Blood Analysis Decision Recruitment Stockholm3 if sampling on referral of PSA Experimental PSA ≥ 1.5-ng/ml Eligible and Primary outcome Sampling of Decision on # csPC consenting referral at Stockholm3 the doctor's participants in primary care discretion Secondary outcome # MRI, # Biopsies, # cnsPC, No previous PC # Benign, Compliance

Figure 1: Phase I design overview

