## Phase II design

Phase II will compare the diagnostic test performance of Stockholm3 (as a reflex to PSA  $\geq$  1.5 ng/ml) to using PSA only. Participants will be 1:1 randomized between control arm with PSA and experimental arm with Stockholm3 as reflex to PSA  $\geq$  1.5 ng/ml. For Phase II, we are thus interested in comparing the test characteristics in isolation (i.e. not Stockholm3's effect on operations, e.g. compliance) and we therefore use randomization on an individual level.

This study phase includes delayed unblinding, meaning that both investigators and participants will remain blinded at the time of blood sampling and will only be unblinded upon receiving the test results. Primary care physicians will recruit men they consider eligible for prostate cancer testing, following standard clinical practice. All participants will undergo blood sampling for both PSA and Stockholm3. Randomization will be performed at the laboratory, and only the assigned test will be analyzed. Men with PSA  $\geq$  3 ng/mL (standard of care) or Stockholm3  $\geq$  11 will be required to undergo further evaluation with MRI.

**Primary Care** Laboratory Primary Care Specialist care Analysis of PSA Referral to MRI if Blood Decision Recruitment R Workup  $PSA \ge 3 \text{ ng/ml or}$ sampling on workup Stockholm3 ≥ 11 Sampling of blood for both Eligible and Referral decision consenting is mandated if participants in PSA and  $PSA \ge 3 \text{ ng/ml or i}$ Analysis of Stockholm3 primary care Analysis Stockholm3 ≥ 11 Primary outcome Stockholm3 if PSA ≥ 1.5-# csPC No previous PC na/ml Secondary outcome # MRI, # Biopsies, # cnsPC, # Benign, Compliance

Figure 2: Phase II design overview

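### Planned operating characteristics over PSA and Stockholm3 cut-offs: work-up is triggered by the test itself, so absolute sensitivity is not identified and will be inflated

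*Protocol*

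**What the plan says.** In the protocol, the secondary outcomes under Phase I Step 6 and Phase II Step 5 both list "Operating characteristics of PSA and Stockholm3 to predict csPC at different PSA and Stockholm3 cut-offs". Two further items in each list do the same for abnormal MRI, defined once as PIRADS ≥ 3 and once as an MRI that led to csPC. None of the three restricts the range of cut-offs or the measures to be reported.

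The outcome needs a biopsy: the primary endpoint is "Number of csPC, defined as Grade Group ≥ 2". The route to biopsy is as follows.

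- **Phase I.** Under Step 4, "This means that the doctor will take decision whether to send men with elevated PSA" (≥ 3 ng/ml, control arm) or elevated Stockholm3 (≥ 11, experimental arm) to MRI. The Phase I design section confirms the discretion: "The decision to refer participants for specialist evaluation, including MRI and biopsy, will be made by the primary care physician". Men with PIRADS ≥ 3 "should be offered prostate biopsy based on current standard of care".
- **Phase II.** Men with PSA ≥ 3 or Stockholm3 ≥ 11 "will be required to undergo further evaluation with MRI", and biopsy is offered at PIRADS ≥ 3.
- **Window.** Phase I Step 5 counts only MRIs and biopsies within 4 months of the result, and Phase II refers back to that data-collection section.
- **Availability of Stockholm3.** It is run in the experimental arm only, as a reflex at PSA ≥ 1.5. For Phase II: "Randomization will be performed at the laboratory, and only the assigned test will be analyzed". The control arm's EDTA tubes are discarded.

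**The concern.** Operating characteristics over a range of cut-offs ordinarily include sensitivity and specificity. Both need disease status in men on either side of the cut-off. Here the test result decides who is worked up, and nothing is planned to establish csPC status in men below the threshold. This is verification bias: cancers that the test misses are largely never seen, so they drop out of the denominator of sensitivity.

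The study's main objective is diagnostic performance, and Phase II is meant to isolate the test characteristics. A published sensitivity near 100%, or a comparison of PSA with Stockholm3 in men selected by Stockholm3, could be read as the trial's answer to that objective. Phase I may be published before Phase II starts, so the issue arises early.

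**Working it through.** **1. Inputs (Study size and outcome).** Phase II assumes csPC detection of 4% v 4.8%, 5% significance, 80% power, 5% dropout and 10,856 men per group. Phase I assumes 4% v 5.6–6.0% and 8,000 men; its central case is a 45% increase (5.8%), m = 100 and ICC 0.008.

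**2. The plan's own figures reproduce.**
- Phase II, two-sided, unpooled variance: n = (1.96 + 0.8416)² × (0.04×0.96 + 0.048×0.952) / 0.008² ≈ 10,313.4, and 10,313.4/0.95 = 10,856. The pooled version gives 10,317, or 10,860 after dropout.
- Phase I central case: design effect 1 + 99×0.008 = 1.792, effective size 4,000/1.792 ≈ 2,232 per arm, power 79.6% (stated 80%). Over the stated ranges power is 56.4–91.9% (stated 58–92%).

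The detection rates can therefore be taken as the plan's working assumptions.

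**3. Naive sensitivity at the referral cut-off.** If no test-negative man is verified, every known csPC lies at or above the cut-off. Sensitivity is then 4.0/4.0 = 100% for PSA ≥ 3 in the control arm, and likewise 100% for Stockholm3 ≥ 11 in the experimental arm.

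**4. Ceiling for the PSA pathway.** Randomisation gives the arms equal expected csPC prevalence, and prevalence is at least what the experimental arm detects. So the sensitivity of the PSA pathway is at most p(control)/p(experimental):
- Phase II: 4.0/4.8 = 83.3%.
- Phase I: 4.0/5.6 = 71.4% to 4.0/6.0 = 66.7% (69.0% at 5.8%).

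At the referral cut-off the naive figure is too high by at least 16.7 points in Phase II. At any control-arm PSA cut-off at or above 3, naive sensitivity is inflated by the same factor, at least 4.8/4.0 = 1.2. The planning rates set no corresponding ceiling for Stockholm3.

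**5. Some discretionary verification changes little.** If 10% of the csPC missed by PSA were found anyway, naive sensitivity would be 4.0/(4.0 + 0.1×0.8) = 98.0% at 4.8% prevalence, or 4.0/(4.0 + 0.1×1.8) = 95.7% at 5.8%.

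**6. Specificity depends on how unverified men are handled.** In verified men only, it is 0% at the referral cut-off, since all are test-positive. If unverified men count as csPC-free, it is (1 − s)/(1 − 0.04), where s is the share with PSA ≥ 3. The protocol does not give s. Assuming s = 10–30% and prevalence 4.8–10%, the naive value runs from 93.8% to 72.9%. The true value is (1 − s − (prevalence − 0.04))/(1 − prevalence). The error is about 0.1 point (s = 10%, prevalence 4.8%: 93.75% v 93.70%) to 1.8 points (s = 30%, prevalence 10%: 72.9% v 71.1%).

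**7. Which cut-offs have verified men.** Stockholm3 cut-offs below 11, and control-arm PSA cut-offs below 3, have essentially none. In the experimental arm, men with PSA 1.5–3 are verified only when Stockholm3 ≥ 11. Men there with PSA ≥ 3 but Stockholm3 < 11 have no clearly planned work-up.

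**8. Consequence for a within-arm comparison.** Among experimental-arm men verified because Stockholm3 ≥ 11, that cut-off has 100% sensitivity by construction, and PSA ≥ 3 can equal but not exceed it. Cancers that PSA would flag and Stockholm3 would miss do not enter the count.

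**The case against.** The strongest reply is that the protocol says operating characteristics and names neither sensitivity, specificity nor a denominator. The statistical section calls itself a summary and defers to a SAP that is not shown here, and positive predictive value fits the wording. This stands in part: the lack of a stated correction method is not a fault of the protocol. But standard corrections for verification bias need verified test-negative men. None are planned in Phase II, and in Phase I they would arise only selectively. An analysis plan cannot create them.

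Several stronger readings are tempting but go beyond the document:

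- **That csPC is verified only in test-positive men.** Phase I referral is discretionary, Phase II does not forbid MRI in other men, and follow-up at 2, 4 and 6 years is mentioned. That follow-up is not linked to this analysis, however, and the 4-month window governs.
- **That no PSA cut-off below 3 has verified men.** Experimental-arm men with PSA 1.5–3 and Stockholm3 ≥ 11 go to MRI; they are selected, not absent.
- **That having Stockholm3 in one arm only is itself a bias.** It is not. Both tests are recorded in the experimental arm at PSA ≥ 1.5, so a comparison exists, though conditional on Stockholm3.
- **That specificity must also be wrong.** It is nearly right if unverified men are counted as csPC-free.
- **That PSA ≥ 3 as a test finds at most about 69% of csPC in Phase I.** That figure is a ratio of pathways and includes compliance, by the protocol's own account of Phase I.

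The phrase joining the two thresholds in Phase II could also mean that either result triggers MRI in the experimental arm. The selection on Stockholm3 would then weaken, but men negative on both tests would stay unverified.

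**Conclusion.** The concern holds for absolute sensitivity and for cut-offs below the referral thresholds. The protocol plans an analysis that its work-up rule cannot support. Sensitivity at the referral cut-off would be reported at or near 100%, against a ceiling of 83% for the PSA pathway under the Phase II planning rates and 67–71% under the Phase I rates. A comparison of the two tests within the experimental arm is selected on Stockholm3 and tends to favour it. The abnormal-MRI analyses share the defect, because MRI also follows the test result.

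The ceilings assume equal prevalence across randomised arms and take the planning rates as true. The 100% assumes that no test-negative man is verified. These are secondary analyses: the randomised primary comparison, the sample size and the data collection are not affected. The change is worth making because it is cheap and governs what may be claimed about test performance.

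**What to change.** In both phases, reword the three operating-characteristics items:

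1. Report positive predictive value (csPC, PIRADS ≥ 3, or MRI leading to csPC, among men worked up) at cut-offs at or above the arm's referral threshold.
2. Label experimental-arm results by PSA range as conditional on Stockholm3 ≥ 11. Reconcile the passages on which result triggers MRI in that arm, so that the label is accurate.
3. Report relative sensitivity through the between-arm csPC detection ratio, which is already the primary analysis.
4. Add the between-arm ratio of men worked up without csPC per randomised man, adjusted for clustering in Phase I. Its components (MRIs, benign biopsies, Grade Group 1 cancers) are already collected.
5. State that absolute sensitivity, and performance at cut-offs below the threshold, are not estimated.

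This needs no new data. The cost is giving up absolute sensitivity and specificity claims. The change should be in place before the Phase I analysis, since that may be published first.
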